1 INTRODUCTION

This document describes the protocol of a pilot stage clinical trial intended to study 8 humans diagnosed with chronic, incomplete, or complete loss of motor function below the level of traumatic spinal cord injury (SCI). The purpose of this trial is to improve the scientific understanding of how two electrical stimulation techniques, one which delivers electricity to the skin surface over the spine (transcutaneous spinal stimulation (TS)) and another which implants temporary percutaneous electrodes into the epidural space of the spinal cord (epidural spinal stimulation (ES)), facilitate spinal circuitry to enable function for individuals with SCI representing all levels of severity. Furthermore, we hope to determine responders versus non responders to spinal stimulation task-specific motor training following a condensed rehabilitation program as well as identify retained effects following 4 months of no intervention. Over the past decade, clinical investigations using either TS or ES have reported positive outcomes, such as regained control of leg movement (Gerasimenko, Lu, et al. 2015; P. S. H. PhD et al. 2011; Angeli et al. 2014; P. J. G. PhD et al. 2017; Gad et al. 2017) and cardiovascular improvements (Phillips et al. 2018; Harkema, Ditterline, et al. 2018; West et al. 2018). Independent investigations of either TS or ES have yielded some knowledge of the interactions between the electric field and spinal cord networks (Minassian, Persy, Rattay, Pinter, et al. 2007; Minassian, Persy, Rattay, Dimitrijevic, et al. 2007; Danner et al. 2016; Hofstoetter et al. 2018; Sayenko, Atkinson, Floyd, et al. 2015; Sayenko et al. 2014; Sayenko, Atkinson, Dy, et al. 2015; Rattay et al. 2000; Danner et al. 2013; Capogrosso et al. 2013).

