This study will include adult humans that sustained a traumatic SCI at least one year before trial enrollment. To qualify for this study, SCI severity must be previously diagnosed with an AIS classified injury. One participant will be enrolled from each AIS classification (A, B, C, and D) for each intervention. All injuries must be located at or above the tenth thoracic vertebrae. Detailed inclusion and exclusion criteria are provided within the appropriate section of this protocol.

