Our Mayo team recorded preliminary TS data in two subjects during supine activities prior to ES implantation. TS-evoked responses were recorded during low-frequency TS to investigate spinal sensorimotor activity generated to produce leg muscle activity. We compared responses across TS and ES. Preliminary data indicate smaller latency from stimulation to response in ES when compared to TS, indicating different mechanisms of action may underlie each approach. However, more subjects need to be investigated with a more structured study design to determine key differences between TS and ES. Completion of the proposed experiments in this protocol will provide data that can be used to improve the scientific understanding of how each technique enables function after SCI. This knowledge will be used to design future investigations that focus on safety and therapeutic efficacy of TS and ES.

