4.1 Inclusion Criteria

- Spinal cord injury due to trauma located at or above the tenth thoracic vertebrae (T10)
- American Spinal Injury Association grading scale of A-D (2 from each) below the level of SCI
- Intact spinal reflexes below the level of SCI
- At least 1-year post-SCI
- At least 22 years of age
- Willing to use medically acceptable methods of contraception, if female and of childbearing potential

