8.2 Statistical Methods

Descriptive Statistics and Graphics

Continuous data will be summarized as median (inner quartile range). Categorical data will be presented as frequency (percentage). Graphical presentations of data will be used for all endpoints. Individual data points will be plotted over time, with distinctions made between data from TS and ES groups. Additionally, associations between measurements prior to and following ES intervention will be assessed using bivariate scatterplots. These associations will be summarized numerically with Spearman's correlation coefficient.

Modeling

The overall ES effect will be assessed by comparing models with and without the treatment indicators. Additionally, measurements taken under various conditions can be modeled simultaneously with appropriate effects for the different conditions. For example, SSEPs will be measured at the tibial and median nerves, each at 2 intensities. Effects for the different locations and intensities will be added to the model, along with effects for the 2 nerves as random effect nested within subject. Models will also be used to quantify associations between assessments at baseline and during the first month, with assessments at the end of the study. This may be used to determine whether there may be markers available to predict which subjects may respond to treatment.

Handling of Missing Data

Mixed modeling will not require complete data collection to conduct the analysis. Other analysis, such as bivariate analyses, which require complete data will be, conducted primarily using complete cases analysis. Sensitivity analyses will be conducted by imputing missing data with predictions from regression models based on baseline data.

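### Section 8.2 seeks markers of response by relating early levels to end-of-study levels, with no baseline-referenced measure specified, so severity tracking can look like a marker when nobody responds

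*Combined protocol and SAP*

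**What the plan says.** Section 8.2 (Modeling) says that models will "quantify associations between assessments at baseline and during the first month, with assessments at the end of the study", and that this may help to show whether there are "markers available to predict which subjects may respond to treatment". No formula is given. The outcome named is a level at the end of the study. Section 1 states the aim behind it: "we hope to determine responders versus non responders to spinal stimulation task-specific motor training". No section gives a threshold or definition of a responder.

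Severity is spread on purpose. Section 1.1: "One participant will be enrolled from each AIS classification (A, B, C, and D) for each intervention". Section 4.1 repeats it as a criterion: "American Spinal Injury Association grading scale of A-D (2 from each) below the level of SCI".

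Three other pieces of the plan bear on the point:

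- Section 8.2 (Descriptive Statistics and Graphics): "associations between measurements prior to and following ES intervention will be assessed using bivariate scatterplots", summarised by Spearman's coefficient.
- Section 8.2 (Handling of Missing Data), for analyses that need complete data: "Sensitivity analyses will be conducted by imputing missing data with predictions from regression models based on baseline data".
- The Study Summary plans repeated-measures ANOVA for change over rehabilitation, but nothing links it to the marker search.

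**The concern.** Response means change. A correlation between an early level and a late level mostly shows whether subjects keep their rank. With two subjects at each AIS grade, a measure that follows severity will tend to order subjects alike at baseline and at the end, whether or not anyone changes. A second measure that also follows severity inherits the association and can then be read as predicting response.

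What is at stake is later work. Section 1.3 says of the study's results: "This knowledge will be used to design future investigations that focus on safety and therapeutic efficacy of TS and ES". Section 1.4.1 adds that they should help decide whether TS is useful for choosing subjects suited to ES. A marker that is only a proxy for severity would mislead that choice.

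**Working it through.** **No figure to reproduce.** The documents give no alpha, power, SD, effect size or tracking correlation. The 5% level is a yardstick, and tracking r = 0.5 / 0.7 / 0.9 is an assumed range. From the documents: n = 8, two per AIS grade, one per grade per arm (Sections 1.1, 4.1 and 8.1).

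**Set-up.** Normal data, no treatment response, 40,000 data sets per setting, t test of the marker coefficient.

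- Second baseline marker: end = r·baseline + √(1−r²)·noise; marker = c·baseline + √(1−c²)·noise.
- AIS only: baseline, end and marker each = √r·AIS score + √(1−r)·noise.
- First-month value of the same outcome: either all visits correlate equally at r, or each visit depends on the one before with correlation r.

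**Why level-on-level flags.** The correlation needed at n = 8 (6 df, t = 2.447) is 2.447/√(2.447² + 6) = 0.71. The marker's true correlation with the end value is c·r. For c = 0.8 that is 0.40 / 0.56 / 0.72. In the AIS-only setting it is √r·√r = r, that is 0.5 / 0.7 / 0.9. None of this involves response.

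**Results: % flagged when nobody responds, at r = 0.5 / 0.7 / 0.9**

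| Marker | Level on level | (a) End on marker, own baseline, arm | (b) Change on marker, arm |
|---|---|---|---|
| Second baseline marker, c = 0.8 | 17 / 32 / 58 | 5 / 5 / 5 | 14 / 10 / 6 |
| Linked only through AIS | 28 / 67 / >99 | 11 / 14 / 16 | 5 / 5 / 5 |
| First-month, equal correlation | 25 / 55 / 94 | 9–10 / 12 / 16 | about 5 |
| First-month, visit to visit | 25 / 55 / 94 | 14 / 22 / 33 | about 5 |

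With c = 0.5 the level-on-level rates are 9 / 13 / 20%, and (a) returns them to 5%. The outcome's own baseline against its end level is flagged in 25 / 55 / 94% (exact Spearman 19 / 41 / 83%).

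**Neither model is clean everywhere.** Model (a) leaves tracking behind when baseline is a noisy copy of severity. Model (b) errs when the marker derives from an error-free baseline. There the covariance of marker and change is c(r−1), or −0.40 / −0.24 / −0.08 for c = 0.8, so the false association is negative. In each row one of the two models is near 5%. A rule that both must flag cannot exceed the smaller rate, so it stays at about 5% or below in every row.

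**Change against the same measure's baseline** is no remedy. Its expected correlation with no response is −√((1−r)/2) = −0.50 / −0.39 / −0.22 (average in samples of 8: −0.48 / −0.36 / −0.21).

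**Check under another error model.** Here stable levels are measured with reliability 0.80 to 0.95, AIS explains 30 / 50 / 70 / 90% of stable variance, and models have no arm term. A separate severity-linked marker is flagged by Spearman in 9–10 / 20–23 / 43–55 / 85–98% with no true change. Own-baseline adjustment gives 5–6 / 5–7 / 6–9 / 10–19%. Change scores give 4.7–5.3% throughout. If AIS explains nothing, the unadjusted rate is about 5%.

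**ES Spearman, n = 4.** With no response it averages 0.39 / 0.57 / 0.78. The smallest two-sided exact p is 2/24 = 0.083.

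**Imputation (side note).** With zero true association and an assumed 1 / 2 / 3 of 8 end values replaced by regression predictions, a linear test flags 10 / 18 / 31% if the predictor is the tested variable. It flags 8 / 12 / 19% if the predictor is correlated 0.8 with it and 6 / 7 / 9% if 0.5. Complete cases give 5%.

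**The case against.** The strongest reply is that the text is silent, not wrong. Section 8.2 lists baseline assessments among the predictors and writes no model, so a joint model could already hold the outcome's own baseline. This stands: a reader might infer that the plan excludes a baseline term, and it does not. But nothing requires one, and the association as worded can be run without it.

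Second, this is a pilot. Sections 3.2 and 3.3 decline to designate formal endpoints, Section 8.1 has no power calculation, no alpha is set for these associations, and individual data are plotted by group. That also stands. The flag rates measure how easily an association arises, not a decision error in a planned test. The passage in Section 1.3 on future studies concerns how each technique enables function, not markers as such.

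Third, an own-baseline covariate is not a cure. Correct: the table shows it failing for AIS-driven and first-month markers, which is why one adjusted model is not enough.

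Two further inferences are not supported. One is that the imputation inflates the marker search: complete cases are primary, imputation is a sensitivity analysis, mixed models do not need it, and it is not shown to reach the marker models. The other is that the pre/post ES Spearman is offered as evidence of response: Section 8.2 places it under descriptive statistics.

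**Conclusion.** The concern holds in this form: the marker search is worded as level on level, its baseline handling is unspecified and response is undefined. Followed as worded, it can report severity tracking as a marker of response.

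The size rests on assumed tracking. It runs from 17 to 58% for a second marker correlated 0.8 with baseline, and from 28 to over 99% if AIS drives everything, against a nominal 5%. The percentages depend on r, c and the error model, but the direction does not as long as the marker follows severity. A reader might infer that every measure will behave this way. The documents give no tracking figure, and a measure unrelated to severity is not affected.

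The consequence is a misleading exploratory marker carried into later work. It is not an error in a main result. It should be corrected before analysis because the change is cheap.

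**What to change.** In Section 8.2:

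1. State that, for the marker search, response means change from the outcome's own baseline.
2. For outcomes with a baseline, replace the level-on-level association with two analyses, one marker at a time: (a) end value on marker with own baseline and arm, and (b) change from baseline on marker with arm. Report both. Call a marker a candidate only if they agree, including in direction.
3. Do not test change against the same measure's own baseline.
4. Report first-month markers separately and rely mainly on (b) for them.
5. Label points by AIS grade in the plots, call the results hypothesis-generating, and describe the pre/post ES Spearman as tracking of levels.
6. Show plots only where there is no baseline or no residual df.
7. As a side change for complete-data sensitivity analyses, replace bare regression predictions with best/worst-value bounds or with multiple imputation that carries residual and parameter variation.

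**Data.** Table 3 as extracted marks EMG, SSEPs, TMS MEPs, mobility tests and surveys at baseline. It marks TS MEPs and ISNCSCI at screening, which Section 6.1 lets serve as baseline. Kinematics and FRT/mFRT first appear at week 1, while Table 1 lists baseline kinematics. The sponsor should reconcile the two tables.

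**Cost.** Mainly wording, plus power. Model (a) fits four parameters, so 8 − 4 = 4 df remain and the partial |r| needed is 2.776/√(2.776² + 4) = 0.81. Power is 17 / 37 / 82% at a true partial r of 0.5 / 0.7 / 0.9. Model (b) leaves 5 df, needing 2.571/√(2.571² + 5) = 0.75. Requiring agreement cannot raise power above that of (a), so fewer associations will appear. If the overground mobility tests cover only AIS C and D (n = 4), (a) has 0 df and those outcomes should be plotted only. Multiple imputation is conservative here (3.3 / 2.5 / 1.7% flagged with 1 / 2 / 3 missing).

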8.3 Subject Population(s) for Analysis

All-completed population: Only subjects who completed all study related procedures and follow-up will be included; however, the PI may adjust this to include a subject who completed the majority of the study visits and procedures.

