Objectives	 a. Identify relationships between stimulation inputs delivered to lumbosacral spinal circuitry and the corresponding electrophysiological outputs, during 4 weeks of motor training with stimulation, and over 16 weeks post-stimulation to determine residual effects, in individuals with SCI. b. Assess motor, sensory, and functional outcomes during 4 weeks of motor training with stimulation, and the retained effects over 16 weeks post-stimulation, in individuals with SCI. 							
Number of Subjects	8 subjects							
Diagnosis and Main Inclusion Criteria	American Spinal Injury Association Impairment Scale A-D							
Study Device	DS8R Isolated Biphasic Constant Current Electrical Stimulator (Digitimer Ltd) Abbott percutaneous trial lead for epidural neurostimulation (Model 3086) Ripple Nomad Neurostimulator							
Duration of Exposure	All subjects will complete either 1 month of transcutaneous spinal stimulation (TS) or temporary epidural spinal stimulation (ES) enabled rehabilitation sessions. Subjects will then be followed for an additional 4 months to complete follow-up assessments.							
Reference therapy	The reference therapy is clinical rehabilitation after SCI.							
Statistical Methodology	Descriptive statistics will be used to describe stimulation-related outcomes for each intervention. Repeated measures analyses of variance will be used to detect changes in outcomes over the course of rehabilitation.							

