1.5 Anticipated Duration of the Clinical Investigation

The anticipated duration of study participation for each human subject is approximately 6 months. During the 6 months, subjects will complete either TS rehabilitation sessions for the 1 month, or ES rehabilitation sessions for 1 month. After 1 month of either TS or ES, subjects will be followed for an additional 4 months for follow-up assessments. ES electrodes will be removed following 1 month of rehabilitation sessions.

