2.1 Primary Objective

The primary outcome data collected will be used to compare spinal sensorimotor activity in muscles below the level of injury during TS or ES-enabled motor tasks in persons with chronic motor complete paralysis of the lower extremities due to traumatic SCI.

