5.7 Masking/Blinding of Study

This is an unblinded study. The PIs, co-investigators, and subjects will know what treatment they received.

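### Section 8.3 analyses completers only, with an open-ended PI exception, and so conflicts with the incomplete-data methods of section 8.2

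*Combined protocol and SAP*

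**What the plan says.** Section 8.3 defines a single population, called all-completed: "Only subjects who completed all study related procedures and follow-up will be included". The sentence continues: "however, the PI may adjust this to include a subject who completed the majority of the study visits and procedures". It gives no number for the majority, does not say whether visits and procedures are counted together or separately, and sets no time for the decision. No all-enrolled, all-treated or safety set is named.

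Section 5.7 states "This is an unblinded study" and adds that the PIs know the treatment received.

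Section 8.2, on missing data, says "Mixed modeling will not require complete data collection to conduct the analysis". It uses complete cases for bivariate analyses and plans regression imputation from baseline data as a sensitivity analysis.

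Section 4.4.1 lists health concerns, non-compliance and study-related SAEs among the factors that may lead to withdrawal. It allows a replacement in the same cohort unless the withdrawal was for a treatment-related AE. Section 8.1 mentions contingency subjects but does not say whether they cover that case. Section 10.1 keeps the right to use data collected before a subject revokes authorization.

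**The concern.** The two statistical sections pull apart. Section 8.2 chooses methods whose purpose is to use subjects with gaps, while 8.3 removes those subjects before the methods are applied unless the PI admits them. Usable data already collected are therefore dropped by default.

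The exception makes matters less clear. It is permissive, it has no threshold, and it can be exercised after outcomes are known by someone who knows the arm.

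Loss may also be related to treatment. Study-related SAEs and health concerns are listed reasons for leaving, and a subject withdrawn for a treatment-related AE is outside both the replacement provision and, by default, the analysis. Each arm has its own route to interruption: lead complications and early explant in the ES arm (5.3), and a halt to stimulation for skin irritation in the TS arm (1.4.2).

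At stake is whether the descriptive picture represents the subjects treated. That matters for a study that states "we hope to determine responders versus non responders to spinal stimulation task-specific motor training" and hopes to inform selection for ES.

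**Working it through.** **Sample size.** One subject per AIS grade per intervention (1.1) gives 4 grades × 2 arms × 1 = 8, which agrees with the stated total and with 4 per arm (5.2). There is no power, alpha or loss figure to reproduce (8.1).

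**Can 'all procedures' be met literally?** Table 3 lists ES MEPs, which do not apply to TS subjects. It lists BBS, TUG and 6MWT, which 6.6.1 describes for motor incomplete injuries. Unless 'as applicable' is read into 8.3, no TS subject completes every listed procedure, and motor complete subjects in either arm may not. The set then depends on the PI clause. With k partial completers the PI can choose among 2^k sets: 2, 4 or 8 for k = 1, 2 or 3.

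**One unreplaced exclusion.** 1/4 = 25% of the arm, and 1/1 = all of that AIS grade in that arm.

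**A subject who misses only week 20 and is not replaced.** Table 3 schedules SSEPs at baseline and weeks 5, 8 and 20.
- Planned SSEP subject-visits per arm: 4 × 4 = 16.
- Default 8.3 drops the whole subject: 16 − 4 = 12, or 12/16 = 75.0%.
- Available data lose one visit: 16 − 1 = 15, or 15/16 = 93.8%.
- Three observed visits are discarded: 15 − 12 = 3.

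**An ES subject lost after week 4.** Section 2.1 aims to "compare spinal sensorimotor activity in muscles below the level of injury during TS or ES-enabled motor tasks". In Table 3, kinematics, EMG, ES MEPs and FRT/mFRT are marked at weeks 1 and 4, giving 4 × 2 = 8 primary-outcome assessments in the stimulation period. All 8 are collected and default 8.3 keeps 0. Table 3 was read from a damaged extraction (Table 1 also shows kinematics at baseline and end), so check this count against the original layout.

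**How often would the rule apply?** The documents give no loss rate. Assume independent loss with probability d per subject, no replacement and no PI exception. The chance of at least one non-completer among 8 is 1 − (1 − d)^8:

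| d (assumed) | P(at least one) |
|---|---|
| 5% | 34% |
| 10% | 57% |
| 20% | 83% |
| 25% | 90% |

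This shows only how readily the rule comes into play. It says nothing about bias.

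**The case against.** The strongest reply is that this is a pilot of 8, with no power calculation, allocation by availability or choice, and mainly descriptive analysis that plots individual data. The PI clause shows that the authors did not intend strict exclusion, and replacement can refill a cohort in many cases. All of that stands and limits the impact. It does not resolve the conflict between 8.2 and 8.3, and small arms make each exclusion count for more.

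A reader might infer more than the documents support:

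- *That every scheduled ES-on recording is finished by week 4, so later visits are irrelevant to the primary comparison.* Section 1.5 says "ES electrodes will be removed following 1 month of rehabilitation sessions", but Table 3 also marks TMS paired with ES or TS at weeks 5, 8 and 20, and 6.6.2 plans urodynamics with the stimulator on, scheduled again after the intervention. These passages must be reconciled with the explant timing. Objective (a) of the Study Summary also runs "over 16 weeks post-stimulation to determine residual effects", and 3.2 declines to designate primary endpoints.
- *That the majority clause contradicts itself, passing a subject lost after week 4 by visits and failing the same subject by procedures.* That depends on leaving out the 12 training sessions. Section 6 is headed as study procedures and contains them, and motor training is a row of Table 3. Once they are counted the contradiction disappears. What remains is an undefined unit.
- *That one exclusion would shift a responder rate by a known amount.* Section 8.2 defines no responder threshold or percentage. It plans associations and possible predictive markers.
- *That the rule favours ES.* Both arms have routes to interruption, and early explant does not by itself mean withdrawal or missed follow-up.
- *That adverse events of non-completers would go unreported.* AEs are recorded for all subjects (9, 9.8), and no text applies 8.3 to them. The gap is only that no AE denominator is stated.

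**Conclusion.** The point holds. Section 8.3 sets a completers-only population with an optional, undefined and untimed exception in unblinded hands, and this undercuts the missing-data methods of 8.2. The size that can be stated is structural: 25% of an arm and one whole AIS grade per unreplaced exclusion, and 12 rather than 15 of 16 SSEP subject-visits when only week 20 is missed. These figures assume the default rule, no replacement and the Table 3 schedule as read.

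The size and direction of any bias cannot be given. If loss is unrelated to outcome there is no expected bias, only discarded data. If it is related, available-data analysis reduces the selection without guaranteeing its removal. This should be fixed before outcome data are reviewed, but it does not threaten a powered conclusion, because none is planned.

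**What to change.** Rewrite 8.3 and adjust 8.2 as follows.

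- **Main set, for all objectives including 16-week retention.** Use all enrolled subjects who began the assigned intervention, with all available visits, and state that the 8.2 missing-data methods apply to this set. Define 'began' identically in both arms, for example at least one stimulation-enabled training session after baseline. Treat testing-only stimulation the same way in each arm. This needs saying because 6.2 and 6.4 count any laboratory visit with stimulation enabled as a session, and Table 3 places TS MEPs at screening.
- **Completers as a sensitivity analysis only.** Word the criterion 'as applicable' to arm and injury grade, state the unit counted, and fix it before outcome data are reviewed. Remove the open PI clause.
- **Withdrawn subjects.** Keep their data. List withdrawals, early explants and replacements by arm and AIS grade.
- **Adverse events.** Summarise over all subjects who started the assigned intervention, including an attempted implant.

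**Cost.** No visits or procedures are added, and most of the change is wording in 8.2 and 8.3. If the completer criterion counts sessions, Table 1 (12 as a minimum) must first be reconciled with 6.2 and 6.4 (12 as a goal), which reaches beyond those sections. So does reconciling the post-explant stimulation entries with 1.5. The downsides are partial data for some subjects, possible loss of the one-per-grade balance when both a withdrawn subject and the replacement are included, and results that may look slightly less favourable.
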